9.1 DATA MANAGEMENT PLAN

A detailed Data Management Plan (DMP) will be established to ensure consistency of the data. This document will include procedures used for data review, database cleaning, and issuing and resolving data queries. If appropriate, the DMP may be updated throughout the study duration. All revisions will be tracked and document controlled.

CRF data will be captured in a validated electronic database management system hosted by St. Jude Medical.

Only authorized site personnel will be permitted to enter the CRF data through the electronic data capture (EDC) system deployed by St. Jude Medical. An electronic audit trail will be used to track any subsequent changes to the entered data.

9.2 DOCUMENT AND DATA CONTROL

9.2.1 Traceability of documents and data

The investigator will ensure accuracy, completeness, legibility and timeliness of the data reported to the sponsor on the CRFs and in all required reports.

9.2.2 Recording data

Source documents will be created and maintained by the investigational site team throughout the clinical study.

The data reported on the CRFs will be derived from, and be consistent with, these source documents, and any discrepancies will be explained in writing.

The CRFs will be validated (eCRF) by the authorized site personnel.

10.0 MONITORING

Centralized monitoring will occur through routine review of real-time data to identify missing data, inconsistent data, data outliers, and potential protocol deviations that may be indicative of systemic and/or significant errors in data collection and reporting at a site as documented in the Data Management Plan. Additionally, copies of event source documents will be reviewed remotely to ensure data quality/validity.

On-site monitoring may occur at the discretion of the sponsor.

11.0 REGULATORY INSPECTIONS

The investigator and/or delegate should contact St. Jude Medical immediately upon notification of a governmental agency inspection at the site. A clinical monitor or designee will assist the investigator and/or delegate in preparing for the audit.

An investigator who has authority to grant access will permit authorized governmental agency employees, at reasonable times and in reasonable manner, to enter and inspect any establishment where devices are held (including any establishment where devices are used or where records or results are kept).

Clinical Investigational Plan

An investigator, or any person acting on behalf of such a person with respect to the study, will permit authorized governmental agency employees, at reasonable times and in reasonable manner, to inspect and copy all records relating to the study.

An investigator will permit authorized governmental agency employees to inspect and copy records that identify subjects, upon notice that governmental agency has reason to suspect that adequate informed consent was not obtained, or that reports required to be submitted by the investigator, to the Sponsor or IRB/EC have not been submitted or are incomplete, inaccurate, false or misleading.

12.0 STATISTICAL CONSIDERATIONS

12.1.1 Sample Size

This is an observational study. No formal power analysis and sample size calculations were performed. Approximately 2000 subjects will be enrolled in this study. To ensure enrollment balance across study centers, no single center will enroll more than 10% of the maximum sample size (200 subjects). A target of 500 ACS subjects will be included in the study.

12.1.2 Analysis Populations

Data from up to 2000 subjects enrolled in this study will be collected and reported. The statistical analyses described in this section will be performed for all enrolled subjects, ACS subjects and stable coronary artery disease subjects separately.

12.1.3 Statistical Method and Analysis

This section describes the statistical method and analysis per subject basis unless otherwise specified. If more than one lesion is measured for a subject, the data analysis may be performed and presented on a per lesion basis, as appropriate.

The following criteria will be used to define the variables per subject level for subject with multiple lesions:

- Treatment decision is defined as “changed” if there is at least one decision change based on FFR for multiple lesions; if none of the decisions has been changed for the multiple lesions, the treatment decision is defined as “unchanged”.
- For all the continuous variables of FFR, resting indices, CFR, contrast FFR, and RRR, we will use the lowest value in all lesions as the value for that variable in each subject. For the continuous variable of IMR, we will use the highest value in all lesions as the value for IMR in each subject.

The following cutoff values will be used to categorize a continuous variable into a binary variable:

- FFR group is defined as “low FFR” if it is equal to or below 0.8 (the cutoff value of 0.8 is selected in line with contemporary guidelines and previous findings¹¹). However, since this is an observational study, there are no mandated cutoff values for this. Therefore, we will also use cutoff value of 0.75¹² in the analysis.
- Resting indices group is defined as “low resting indices” if it is equal to or below 0.86 (the cutoff value of 0.86 is selected based on previous findings that a baseline Pd/Pa \leq 0.86 is associated with a positive predictive value of 100% for FFR measurement¹³). We will also use the cutoff value of 0.92¹⁴ in the analysis.

Clinical Investigational Plan

- CFR is defined as “low CRF” if it is below 2.0 (the cutoff value of 2.0 is selected based on previous findings^{15,16}).
- IMR is defined as “high IMR” if it is equal to or above 25 (the cutoff value of 25 is selected based on previous findings¹⁷).
- Contrast FFR is defined as “low Contrast FFR” if it is equal to or below 0.83 (the cutoff value of 0.83 is selected based on previous findings¹⁸).
- RRR is defined as “low RRR” if it is smaller than 2.0 (the cutoff value of 2.0 is selected based on previous findings¹⁹).

The following statistical analysis will be performed for each of the study objectives:

1. Characterize the frequency of change in treatment plan when FFR is used compared to the initial decision based on angiography alone

Frequency and percentage of change in treatment decisions when FFR is used compared to the initial decision based on angiography alone will be presented both per subject level and per lesion level.

2. Characterize the 12-month clinical outcomes (MACE) in subjects in whom the use of FFR did not lead to a change in treatment decision vs. subjects in whom the use of FFR led to a change in treatment decision.

12-month MACE event rate will be summarized using frequency and percentage. Fisher Exact test will be performed to evaluate the association between 12-month MACE event and prospective treatment decisions, i.e. change or no change, based on FFR measurements. A repeated measures logistic regression with generalized estimating equations (GEE) per lesion level will be performed if needed.

3. Characterize the 12 month clinical outcomes (MACE) by FFR values and resting indices respectively.

Fisher Exact test will be performed to evaluate the association between 12-month MACE event and binary FFR and binary resting indices variables respectively using the following FFR and resting indices groups:

- 1) Low FFR group ($FFR \leq 0.8$) and high FFR group ($FFR > 0.8$).
- 2) Low FFR group ($FFR < 0.75$) and high FFR group ($FFR \geq 0.75$).
- 3) Low resting indices group ($Pd/Pa \leq 0.86$) and high resting indices group ($Pd/Pa > 0.86$).
- 4) Low resting indices group ($Pd/Pa \leq 0.92$) and high resting indices group ($Pd/Pa > 0.92$).

A repeated measures logistic regression with generalized estimating equations (GEE) per lesion level will be performed if needed.

A logistic regression will be performed to evaluate the association between 12-month MACE event and continuous FFR and continuous resting indices respectively. A repeated measures logistic regression with generalized estimating equations (GEE) per lesion will be performed if needed.

4. Compare resting indices with FFR values.

Kappa coefficient will be used for binary variables, and correlation will be used for continuous variables to examine agreement between FFR values and resting indices.

5. Characterize the 12 month clinical outcomes (MACE) by other PressureWire-derived indices (CFR, IMR, contrast FFR, RRR).

Clinical Investigational Plan

Fisher Exact test will be used for binary variables, and logistic regression will be used for continuous variables to evaluate the association between 12-month MACE event and other PressureWire-derived indices (CFR, IMR, contrast FFR, RRR) respectively.

6. Compare other PressureWire-derived indices (CFR, IMR, contrast FFR, RRR) with FFR values

Kappa coefficient will be used for binary variables, and correlation test will be used for continuous variables to examine agreement between FFR values and other PressureWire-derived indices (CFR, IMR, contrast FFR, RRR) respectively.

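### Objectives 4 and 6 have no same-lesion pairing rule, so kappa and correlation can compare FFR from one lesion with an index from another, and correlation is presented as agreement

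*Combined protocol and SAP*

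**What the plan says.** The default unit is the subject: "This section describes the statistical method and analysis per subject basis unless otherwise specified". For subjects with more than one measured lesion, section 12.1.3 adds that "the data analysis may be performed and presented on a per lesion basis, as appropriate".

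The subject-level value is set one variable at a time. For FFR and every other index except IMR, "we will use the lowest value in all lesions as the value for that variable in each subject". IMR goes to the other extreme: "For the continuous variable of IMR, we will use the highest value in all lesions as the value for IMR in each subject".

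The objectives differ in what they say about lesions:

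- **Objective 1:** results "will be presented both per subject level and per lesion level".
- **Objectives 2 and 3:** "A repeated measures logistic regression with generalized estimating equations (GEE) per lesion level will be performed if needed".
- **Objective 4:** "Kappa coefficient will be used for binary variables, and correlation will be used for continuous variables to examine agreement between FFR values and resting indices". No unit, pairing rule or clustering method is given.
- **Objective 6:** kappa again, and a "correlation test will be used for continuous variables to examine agreement between FFR values and other PressureWire-derived indices". Again no unit, pairing rule or clustering method.

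Under section 6.4, Pd/Pa and adenosine FFR are collected for all evaluated lesions. IMR, CFR and contrast FFR are optional and depend on local practice and equipment. Measurements may come from index or secondary procedures; the footnote to Table 1 in section 6.2 mentions this only for ACS patients.

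**The concern.** Whether an index agrees with FFR is a question about a lesion. If lesion A has a subject's lowest FFR and lesion B the lowest CFR, the default analysis pairs FFR from A with CFR from B. For IMR it pairs opposite extremes. Nothing requires the two values to come from the same procedure either.

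Two distortions follow, and they can act in opposite directions. Pairing across lesions weakens a true relationship. Mixing subjects with different lesion counts creates one, because every index becomes more extreme as more lesions are searched. Where an optional index exists for only some of a subject's lesions, the lowest FFR may come from a lesion in which the index was never measured.

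A separate point applies whatever the lesion count: for continuous variables both objectives use correlation to examine agreement, which it does not measure.

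At stake is whether the reported kappa and r can be read as how well an index stands in for FFR in a given lesion.

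**Working it through.** The plan states no kappa, correlation, lesion count or uptake figure, so there is no figure of its own to reproduce. Everything below is illustration.

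**Assumptions (none from the documents).** Lesion values are bivariate normal. Subjects have 1/2/3 lesions in 60/25/15% or 75/20/5%. The within-subject ICC is 0 or 0.2. Of lesions, 30, 40 or 50% are positive on each index. Simulations used 400,000 subjects per scenario.

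**1. How often lesions are crossed.** With two lesions and lesion-level correlation r, the chance that the two lowest values come from different lesions is arccos(r)/π: 14% at r = 0.9, 21% at 0.8, 40% at 0.3 and 50% at 0. For lowest FFR against highest IMR it is 1 − arccos(r)/π: 50% at r = 0.

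**2. Objective 4 (Pd/Pa in every lesion, lesion r 0.75).** Simulated subject-level r is 0.76, and kappa rises by 0.01 to 0.02. Of all subjects, 6-11% contribute a cross-lesion pair. The small net change is partly cancellation. If instead every subject had two lesions (ICC 0), a lesion r of 0.80 would give a subject-level r of 0.75.

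**3. Objective 6, index truly unrelated to FFR, measured in every lesion.** The minimum of 1, 2 or 3 standard normal values has mean 0, −0.5642 or −0.8463 and variance 1, 0.6817 or 0.5595. Let B be the variance of these means over lesion counts and W the average of the variances. Then

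r = (1 − ICC)B / [(1 − ICC)B + ICC + (1 − ICC)W].

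For 60/25/15:

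- mean = −(0.25 × 0.5642 + 0.15 × 0.8463) = −0.2680
- B = 0.25 × 0.5642² + 0.15 × 0.8463² − 0.2680² = 0.1870 − 0.0718 = 0.1152
- W = 0.60 + 0.25 × 0.6817 + 0.15 × 0.5595 = 0.8543
- ICC 0: r = 0.1152/0.9695 = 0.12
- ICC 0.2: r = 0.0921/0.9756 = 0.09

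For 75/20/5, B = 0.0754 and W = 0.9143, giving r = 0.08 and 0.06. So r is 0.06-0.12 when the true value is 0. For FFR minimum against IMR maximum the size is the same and the sign negative.

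For kappa at ICC 0, let P be the chance that a subject is positive given the lesion count; then kappa = Var(P)/[p(1 − p)], with p the mean of P. The largest case is 60/25/15 with 50% of lesions positive: P = 0.50, 0.75, 0.875; p = 0.6188; Var(P) = 0.0226; kappa = 0.0226/0.2359 = 0.10. Over all settings, including ICC 0.2, simulation gives 0.04-0.10.

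The artefact is the same if each subject has all or none of their lesions measured. With a random half of lesions measured, |r| is 0.03-0.05. With one random lesion per subject, or only the lowest-FFR lesion, it is 0.

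Objective 6 names a correlation test. The null standard error of r is about 1/√n: 0.022 at n = 2000 and 0.045 at n = 500. At a two-sided 5% level (not stated in the plan) the thresholds are 1.96 × 0.022 = 0.04 and 1.96 × 0.045 = 0.09. If uptake approached these numbers, the artefact could reach significance at 2000, and its upper end at 500.

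**4. Objective 6, contrast FFR (assumed lesion r 0.90, kappa about 0.71).**

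| Where contrast FFR is measured | Subject-level r | Subject-level kappa |
|---|---|---|
| Every lesion, all or none of a subject's lesions, or lowest-FFR lesion only | 0.90 | 0.70-0.72 |
| One random lesion in 10% of multi-lesion subjects, rest complete | 0.88-0.89 | 0.69-0.71 |
| Same, 25% | 0.85-0.88 | 0.67-0.70 |
| Same, 50% | 0.80-0.85 | 0.63-0.67 |
| Random half of all lesions | 0.74-0.82 | 0.57-0.64 |
| One random lesion in every subject | 0.71-0.81 | 0.54-0.63 |

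**5. Correlation against agreement.** If one measure equals the other plus a constant d, r = 1.00, but Lin's concordance coefficient is 2s²/(2s² + d²). With an assumed SD s = 0.10, d = 0.05 gives 0.02/0.0225 = 0.89, and d = 0.10 gives 0.02/0.03 = 0.67.

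**The case against.** The strongest reply is that the plan already permits a lesion-level analysis when several lesions are measured, and that this permission covers all six objectives. That is true, but it leaves the choice open until the data are seen. Objective 1 shows that the authors could require both levels when they wanted to. The contrast with Objectives 2 and 3 is weaker, since their lesion-level model is itself conditional.

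Four further points have weight:

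- **Objective 4** hardly moves, because Pd/Pa and FFR are collected in every evaluated lesion. This stands, and it is why the concern is mainly Objective 6.
- **The larger contrast-FFR losses** need measurement in haphazardly chosen lesions. Uptake driven by operator or equipment could well be all or none within a subject, and then there is no loss. Nothing in the documents indicates random selection, and nothing rules out partial uptake.
- **The subject-level question is legitimate**: does a subject's worst FFR classify them as their worst index does? That justifies keeping it under its own label, but it is not lesion-level agreement.
- **Kappa is an agreement measure and is already planned**, and correlation is a reasonable summary for CFR and IMR, which are not on the FFR scale. The correlation point is therefore largely wording, plus one useful addition for contrast FFR.

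The study is observational, has no formal power calculation, and attaches no decision rule to these objectives. That limits the consequences.

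**Conclusion.** The concern holds as a specification gap: followed as written, the plan can pair different lesions and possibly different procedures. The reading of the text is secure. The size is not, because it depends on assumed lesion counts, ICC and uptake. Objective 4 is essentially unaffected in pooled data. For Objective 6 the effect ranges from nothing to a modest spurious association for an unrelated index, or an appreciable understatement for contrast FFR if it is measured in only some lesions. Weakly related indices lie between these cases, with either direction possible. Subjects with one measured lesion are unaffected by cross-lesion pairing. The effect of mixing procedures was not quantified. The plan should be changed, mainly because the change is cheap and removes a choice that could otherwise be made after seeing the data.

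**What to change.** In section 12.1.3, for Objectives 4 and 6:

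- Make the lesion the primary unit. Pair each index with FFR from the same lesion and the same procedure, use only lesions with both values, and report the number of pairs and of subjects.
- Give subject-clustered intervals for kappa and r, for example from a bootstrap that resamples subjects.
- Keep the lowest/highest subject-level comparison as a labelled secondary analysis, in line with the two levels reported for Objective 1.
- Describe r as association. For contrast FFR against FFR, which share a scale, add the mean difference with limits of agreement that allow for several lesions per subject.

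The cost is SAP wording and a little programming. No new data are needed: Pd/Pa and FFR are already collected for every evaluated lesion, and Objective 6 would use whichever lesions have both values. This assumes that the case report forms, which are held under separate cover, link each value to its lesion and procedure.

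### Objective 2 compares MACE by changed v unchanged decision without regard to direction, so opposite results can cancel; add a MACE table by initial plan and post-FFR decision

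*Combined protocol and SAP*

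**What the plan says.** Section 3.3 words objectives 2, 3 and 5 as characterizing 12-month MACE, and section 12.1.1 states that no power calculation was made.

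For objective 2, section 12.1.3 gives crude MACE percentages, and then a "Fisher Exact test will be performed to evaluate the association between 12-month MACE event and prospective treatment decisions, i.e. change or no change". For a subject with several lesions the decision is changed "if there is at least one decision change based on FFR for multiple lesions"; otherwise it is unchanged. Direction plays no part in the definition.

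For objective 3, a "Fisher Exact test will be performed to evaluate the association between 12-month MACE event and binary FFR and binary resting indices variables respectively", with FFR cutoffs of 0.80 and 0.75 and Pd/Pa cutoffs of 0.86 and 0.92. For FFR and the other indices except IMR, "we will use the lowest value in all lesions as the value for that variable in each subject"; for IMR, "we will use the highest value in all lesions as the value for IMR in each subject". Section 3.2 anticipates 0.80 as the decision threshold but does not mandate it.

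For objectives 2 and 3 the section adds: "A repeated measures logistic regression with generalized estimating equations (GEE) per lesion level will be performed if needed". Where several lesions are measured, "the data analysis may be performed and presented on a per lesion basis, as appropriate". Objective 5 uses Fisher tests and logistic regression to "evaluate the association between 12-month MACE event and other PressureWire-derived indices (CFR, IMR, contrast FFR, RRR) respectively", with no lesion-level model named.

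The planned populations are all, ACS and stable subjects (section 12.1.2). Section 12.1.4 breaks MACE down by component only. Section 6.4 requires the initial plan to be documented before FFR.

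**The concern.** A change to deferral and a change to revascularization are opposite clinical courses, and nothing says that they carry the same MACE risk. Pooled, their rates average. If one lies above and the other below the unchanged rate, the comparison can come out flat. The unchanged group has a similar mixture: planned and confirmed deferral together with planned and confirmed revascularization. Objective 2 would then report a null that could mean either no difference or two differences that offset each other.

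Two lesser points concern interpretation. The first FFR cutoff in objective 3 is also the anticipated decision threshold, so that contrast mixes the risk that FFR marks with the treatment that it prompted. In addition, the any-change and lowest-value rules make group membership more likely as more lesions are measured.

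**Working it through.** The only derived figure in section 12 is the per-centre cap, 0.10 x 2000 = 200, which reproduces and has no bearing here. No MACE rate, change rate, lesion mix or alpha is given. From the documents come N = 2000, 500 ACS subjects, the two subject-level rules and the 0.80 threshold. Every other input below is an assumption.

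**1. Share changed.** Assume 60/30/10% of subjects have 1/2/3 lesions and each lesion has a 30% chance of a changed decision. P(changed | k lesions) = 1 - 0.7^k = 30/51/66%. Overall this is 0.6 x 0.30 + 0.3 x 0.51 + 0.1 x 0.657 = 0.399, or about 800 of 2000.

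**2. Direction.** Assume an even split, MACE of 3% and 9% in the two directions, and 6% in unchanged subjects. Confidence intervals are Clopper-Pearson.

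| Group | Events/n | MACE | 95% CI |
|---|---|---|---|
| Changed, direction A | 12/400 | 3.0% | 1.6-5.2% |
| Changed, direction B | 36/400 | 9.0% | 6.4-12.2% |
| Changed, pooled | 48/800 | 6.0% | 4.5-7.9% |
| Unchanged | 72/1200 | 6.0% | 4.7-7.5% |

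In simulation with a two-sided 0.05 Fisher test, changed v unchanged rejects in about 5% of runs and direction A v B in about 95%. With 600 changed instead of 800, the figures are about 5% and 85 to 86%.

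Sensitivity, with 600 changed:
- At 4% v 8%, the pooled test rejects in about 4% and the split in 48%.
- With 30% of changed subjects in the 9% direction, the pooled rate is 0.3 x 9% + 0.7 x 3% = 4.8%. Cancellation is then partial, and the pooled test rejects in about 15%.

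In 500 ACS subjects with 200 changed, the split is 3/100 (0.6-8.5%) and 9/100 (4.2-16.4%), and the intervals overlap.

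**3. Mixed directions.** With half of the changes each way, P(lesions changed in both directions | k) = 1 - 2(0.85)^k + 0.70^k = 0/4.5/11.5%. Overall this is 2.5%, about 50 subjects or 6% of those changed. Step 2 ignores them; the table should not.

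**4. Objective 3 at 0.80.** Assume untreated MACE of 10% (low FFR) and 5% (high FFR), an odds ratio (OR) of 2.11. Low-FFR subjects are revascularized with probability a and high-FFR subjects with probability 1 - a; treatment multiplies risk by r.
- Low: 0.10 x ((1 - a) + a x r). High: 0.05 x (a + (1 - a) x r).
- At a = 0.95 and r = 0.5: 5.25% v 4.88%, OR 1.08.
- For r = 0.7/0.5/0.4, the OR is 1.49/1.08/0.88 at a = 0.95, 1.61/1.26/1.08 at 0.85 and 1.73/1.46/1.31 at 0.75.

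Simulated at the 0.75 cutoff, with a = 0.95 and r = 0.5, an untreated OR of 2.07 appears as 1.32, so the distortion is smaller. Pd/Pa was not computed.

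**5. Cell sizes for that display.** Take lesion FFR as independent normal, mean 0.81, SD 0.10. P(lowest <=0.80) is 46/71/84% for 1/2/3 lesions, 57.3% overall. At a = 0.95, low-FFR deferred subjects number 2000 x 0.573 x 0.05 = 57 (about 6 events). High-FFR treated subjects number 2000 x 0.427 x 0.05 = 43 (about 1 event at r = 0.5). In ACS the cells are 14 and 11, with 1.7 events expected in all.

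**6. Lesion count.** Assume MACE of 5/8/12% for 1/2/3 lesions and no effect of change within a count. Weighting by P(changed | k), the subject-level rates are 7.3% v 6.1%, RR 1.19, and Fisher rejects in about 16% of runs. Without a gradient the RR is 1.00. At lesion level, changed and unchanged lesions share one rate: (0.6 x 1 x 5% + 0.3 x 2 x 8% + 0.1 x 3 x 12%) / 1.5 = 11.4% / 1.5 = 7.6%, RR 1.00. A GEE with independence working correlation and robust standard errors rejected in 5.5% of 600 runs, close to nominal.

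**The case against.** The plan claims little. Its objectives characterize, its tests concern association, no covariates are named, and no power is asserted. A reader might infer that the Fisher tests are wrong, or that the plan claims an effect of FFR guidance on outcome. The documents support neither: crude MACE by group is a fair answer to the objectives as worded. An explicit descriptive label would therefore add little.

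A reader might also infer that the lesion-level GEE helps with none of these problems, since MACE is a subject-level outcome repeated for each lesion. For lesion count that is wrong. The artefact comes from collapsing lesions to any change or lowest value, and a lesion-level model avoids both rules when change or FFR per lesion does not depend on lesion count (step 6). The GEE does not help with direction, because its exposure is still change or no change.

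It is fair, too, that all the rates are assumed, that 3% v 9% was chosen to show cancellation, and that MACE by treatment decision stays confounded and sparse. These points limit the secondary displays. They do not answer the main one: pooling of directions follows from the written definition, whatever the rates. Optional per-lesion presentation does not commit the plan to a MACE table by direction.

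**Conclusion.** The point holds for objective 2. As defined, changed v unchanged cannot distinguish no difference from opposite differences. That conclusion needs no assumed rate; the size does. Under the 3%/9%/6% assumptions the pooled test has almost no chance of showing what the split shows in about 85 to 95% of full-cohort studies. Smaller or uneven differences narrow the gap, and the ACS subgroup would show it only imprecisely.

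The other two points are secondary. At the 0.80 cutoff, an untreated OR of 2.11 could appear as anything from 0.88 to 1.73 over the assumed range. It would go too far to infer that every objective 3 contrast is dominated by treatment: 0.80 is anticipated rather than mandated, and neither 0.75 nor the Pd/Pa cutoffs are the anticipated threshold. The lesion-count effect is modest and exists only if MACE varies with lesion count, which the documents do not say. No redesign or change in sample size follows.

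**What to change.** 1. Objective 2: keep the planned comparison. Add 12-month MACE with 95% CIs by initial plan and post-FFR decision, in five categories: unchanged deferred, unchanged revascularized, changed to deferral, changed to revascularization, and lesions in mixed or opposite directions.
2. Fix the category at the decision made immediately after the FFR measurement. Admission with urgent revascularization is a MACE component (section 8.2) and secondary procedures are in scope (section 6.4). Without a time point, the outcome itself could move a subject from deferred to revascularized.
3. Objective 3, secondary: show MACE with 95% CIs by FFR group within that same decision category (deferred v revascularized). State that these comparisons are unadjusted and remain confounded.
4. Lesion count: show MACE by number of lesions measured, or run the lesion-level GEE for objectives 2 and 3 routinely instead of only if needed.

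The cost is some SAP wording and a few tables, best specified before the final analysis. Off-diagonal cells will be sparse and intervals wide, especially in the 500 ACS subjects, so rates with intervals suit better than further tests. The initial plan, lesion measurements and PCI details appear to be collected (sections 6.2 and 6.4). However, the treatment-plan categories are not defined and the CRFs are under separate cover (Appendix G), so those fields need checking first.

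### The all-enrolled association analyses for objectives 2, 3 and 5 are not stratified or adjusted for ACS versus stable presentation, so the pooled result alone is open to confounding by case mix

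*Combined protocol and SAP*

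**What the plan says.** Section 12.1.2 sets out three analysis sets: "The statistical analyses described in this section will be performed for all enrolled subjects, ACS subjects and stable coronary artery disease subjects separately". The synopsis and section 3.3 apply the same split to every objective.

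Section 12.1.1 gives the composition: "Approximately 2000 subjects will be enrolled in this study", and "A target of 500 ACS subjects will be included in the study". No upper limit on ACS subjects and no number for stable subjects is stated. The section also says "No formal power analysis and sample size calculations were performed".

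The methods in section 12.1.3 are:

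- Objective 2: "Fisher Exact test will be performed to evaluate the association between 12-month MACE event and prospective treatment decisions, i.e. change or no change". No subject-level logistic model is planned.
- Objective 3, binary: "Fisher Exact test will be performed to evaluate the association between 12-month MACE event and binary FFR and binary resting indices variables respectively".
- Objective 3, continuous: "A logistic regression will be performed to evaluate the association between 12-month MACE event and continuous FFR and continuous resting indices respectively".
- Objective 5: a Fisher test for each binary index and logistic regression for each continuous index (CFR, IMR, contrast FFR, RRR).
- Objectives 2 and 3 also allow a per-lesion GEE logistic model if needed. It deals with several lesions in one subject and has no stated term for presentation.

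Sections 12.1.1 to 12.1.5 name no stratification factor, covariate or interaction test. That the logistic models hold a single variable is inferred from this silence and from the plan taking the indices one at a time.

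**The concern.** The plan regards ACS and stable disease as different enough to analyse apart, yet in the all-enrolled set it collapses them into one 2x2 table or one single-index model. Presentation is a confounder of that pooled association if it is related both to 12-month MACE and to the exposure. The pooled odds ratio then blends the association within each group with the difference between groups. This can produce an association that neither group has, or hide one that both have.

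The blend also depends on how many ACS subjects are recruited, which the target influences. The plan does not say which of the three results leads, or how to read a pooled signal that neither group supports.

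**Working it through.** **Inputs from the plan.** Total about 2000; ACS target 500, so 500/2000 = 25% if the target is met exactly, leaving 1500 stable. The plan states no power, event count or effect size, so there is no figure of its own to reproduce.

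**Assumed inputs.** MACE rates by presentation, exposed share by presentation, and two-sided alpha 0.05. None is in the documents. Exposure means low index or changed decision.

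**Formula.** Let n be group size, m the MACE rate and e the exposed share (A = ACS, S = stable), with no association inside either group:

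- Risk in exposed: p1 = (nA·eA·mA + nS·eS·mS) / (nA·eA + nS·eS)
- Risk in unexposed: p0 = the same with 1 − e in place of e
- Pooled OR = [p1/(1 − p1)] / [p0/(1 − p0)]

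If mA = mS, or if eA = eS, then p1 = p0 and the pooled OR is exactly 1. Both must differ for an artefact to appear.

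**Worked case.** MACE 10% ACS, 4% stable; exposed 55% and 40%. Exposed: 275 + 600 = 875 subjects, 27.5 + 24 = 51.5 expected events. Unexposed: 225 + 900 = 1125 subjects, 22.5 + 36 = 58.5 expected events. OR = (51.5/823.5)/(58.5/1066.5) = 1.14, although the OR is 1 in each group.

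**Range.** Rejection rates are from 3000 simulated studies per scenario; two figures come from two independent runs. The simulation standard error is about 0.4 points near 5% (√(0.05 × 0.95/3000)) and 0.7 points near 19%.

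| MACE, ACS / stable | Exposed, ACS / stable | Events / exposed | Events / unexposed | Pooled OR | Pooled Fisher rejects | Stratified Mantel-Haenszel rejects |
|---|---|---|---|---|---|---|
| 8% / 5% | 50% / 40% | 50/850 | 65/1150 | 1.04 | 4.2-5.0% | 4.0% |
| 10% / 4% | 50% / 40% | 49/850 | 61/1150 | 1.09 | 6.5% | 4.7% |
| 10% / 4% | 55% / 40% | 51.5/875 | 58.5/1125 | 1.14 | 8.8-9.7% | 5.2% |
| 10% / 4% | 60% / 35% | 51/825 | 59/1175 | 1.25 | 18.7-18.9% | 5.1% |
| 12% / 4% | 60% / 30% | 54/750 | 66/1250 | 1.39 | 38% | 5% |

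The last row is a stronger imbalance: MACE three times as high and exposure twice as common in ACS.

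**Opposite direction.** With MACE 8% and 4% but exposure less common in ACS (45% and 55%), exposed events are 18 + 33 = 51 of 1050 and unexposed events 22 + 27 = 49 of 950. OR = (51/999)/(49/901) = 0.94. A mix of this kind would partly mask a real positive association.

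**Dependence on the mix.** With MACE 10% and 5%, exposure 60% and 30%, and no association in either group, the pooled OR is 1.12, 1.22, 1.24 and 1.15 for 200, 500, 1000 and 1500 ACS subjects out of 2000.

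**Not checked.** The continuous-index logistic models and the GEE models were not simulated. The same reasoning applies to them, but the figures above are for binary exposures.

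**The case against.** The strongest reply is that the plan already contains the unmixed results. Separate ACS and stable analyses are mandatory for every objective, so a pooled association absent from both groups would be visible in the same report. This stands, and it confines the problem to the pooled result. It does not remove it. The separate analyses have less power: assuming equal exposure groups, about 56% in ACS for 5% versus 10% MACE (250 per group), and 80% in stable for 3% versus 6% (750 per group). A pooled signal without group signals could therefore be low power or case mix; a stratified pooled estimate helps tell these apart.

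Second, the size is wholly assumed, and so is its direction. This also stands. The one direct comparison in the background (section 2.0) reports similar microcirculatory vasodilatory capacity in non-ST-elevation infarction and stable angina. It does not concern FFR, but it lends no support to a large exposure gap for the microcirculatory indices of objective 5.

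Third, the study is observational, has no stated alpha and aims to characterize. A crude all-comers association is a legitimate description of the recruited sample, and the rejection rates above count as errors only if the presentation-adjusted association is the target. This supports keeping the crude result as descriptive. It does not support leaving it as the only pooled analysis, since association tests are planned and the crude value moves with recruitment.

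Fourth, a reader might infer that a test of difference between ACS and stable is missing. No objective asks whether the groups differ, so its absence is not a gap against the plan's aims. Such a test would also be weak: about 41-45% power for an odds ratio of 2 in ACS against 1 in stable (Wald approximation, assumed MACE 8-10% and 4-5%).

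**Conclusion.** The point holds for the pooled set only. The all-enrolled analyses of objectives 2, 3 and 5 are crude with respect to presentation, and under differing MACE and exposure they could show, or hide, an association through case mix alone. Under the assumed rates the effect runs from negligible (OR 1.04, rejection 4-5%) to moderate (OR 1.25, about 19%), and it goes further only with stronger imbalance. The true size cannot be known from the documents.

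Two stronger readings are tempting and not supported. One is that any pooled association must be an artefact: the arithmetic shows only that one could arise solely from the mix, and a real within-group association is not excluded. The other is that a quota creates the problem: 500 ACS is a target without a cap, it does not fix the share at 25%, and the same confounding would occur if the mix came from ordinary practice. It is also unsupported to predict which of the three results readers will quote. This is an inexpensive improvement to the pooled analysis, not a defect in the study as a whole.

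**What to change.** Add to section 12.1.3:

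- For all enrolled subjects, test binary associations in objectives 2, 3 and 5 with an exact Cochran-Mantel-Haenszel test, and report the common odds ratio, stratified by presentation (ACS/stable).
- Include presentation as a covariate in the all-enrolled logistic models (objectives 3 and 5) and in any all-enrolled GEE model (objectives 2 and 3).
- The crude pooled result may be kept, labelled descriptive.
- Keep the separate ACS and stable analyses as planned.
- An exposure-by-presentation interaction may be reported as exploratory, with its low power noted so that a non-significant result is not read as homogeneity.

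The cost is a change of wording and minor programming. Presentation is part of the first inclusion criterion and already defines the analysis sets, so nothing new is collected. Power is essentially unchanged: with exposure balanced across presentation and a true odds ratio of 1.6, the exact stratified test and the pooled Fisher test reached 71% and 70% in simulation. Stratification removes confounding by presentation only; other confounders remain.
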